9.3 Variables

A questionnaire will be developed to elicit responses measuring physician knowledge and understanding of the key information included in the revised SmPC and DHPC for CPA monotherapy. This questionnaire will contain closed-ended questions (e.g., multiple choice, true/false) with no free-text response fields, eliciting responses measuring physician knowledge and understanding of the key information in the revised SmPC and DHPC for CPA monotherapy. The physician questionnaire will include items in the following content areas:

- Approved indications of CPA monotherapy
- Occurrence of meningiomas in association with CPA monotherapy
- Contraindications relevant to meningioma
- Signs and symptoms of meningioma
- Restriction of the indication to second-line treatment

- Approved dosing (i.e., treatment should be prescribed for the shortest possible time and with the lowest effective dose)
- Risk factors associated with meningioma (i.e., risk increases with increasing cumulative doses)

The questionnaire will also include the following items to investigate physician receipt and use of the DHPC and revised SmPC:

- Receipt and review of the DHPC and SmPC
- Estimated time between the physicians' review of the DHPC and SmPC and completion of the survey

In addition, the physician questionnaire will include queries on the following items to characterise the physicians and their practices:

- Physicians' practice setting
- Average number of CPA monotherapy prescriptions each month
- Years in practice
- Gender
- Age

Because approved indications and dosing vary by country, adaptations may be made to the questionnaire to ensure that it is specific and applicable to the country where it is being administered.

The questionnaire is anticipated to take 10 to 15 minutes to complete and will be administered in the local language for each country. The questionnaire will be administered electronically and programmed so that respondents will not be able to move backward in the survey to change their answers to previous questions.

The draft version of the questionnaire is included in Annex 3.

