Survey results will be stratified on selected variables (e.g., age, gender, practice setting, type of physician) to see whether an imbalance of the characteristics of responders versus nonresponders could cause a bias in the overall study results. An imbalance would lead to a bias in the knowledge results only if there were differences in knowledge between the different levels of the imbalanced characteristic. For example, if the study sample includes a much higher percentage of males than that of the overall population of each specialty, an examination of knowledge by gender will identify whether this imbalance would cause a bias in the overall results. If the stratified results show that knowledge is similar by gender, the imbalance should not bias the overall results.

In addition to the stratification performed to assess responder bias, the overall results tables of the knowledge questions will be stratified by other variables (e.g., number of years treating patients, time between when the physicians reviewed the prescriber guide and took the survey, average number of prescriptions of CPA monotherapy each month) to identify whether any of these variables have an impact on knowledge.

Typically, questionnaire data are mostly complete, and each question will be analysed individually among those participants who respond. The analysis population will consist of respondents who were eligible for the study, provided informed consent, and completed at least one of the knowledge questions. No imputation of missing data will be performed.

All analyses will be performed using SAS version 9.4 (or higher) statistical software. Programmes, logs, and output will be reviewed for accuracy according to relevant standard operating procedures.

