9.9 Limitations of the research methods

As with all cross-sectional surveys that depend on health care professionals agreeing to participate, some limitations are inherent. Many methodologic and operational challenges are well recognised (7). Although the study is designed to select a diverse and generally representative sample of physicians who have recent experience with CPA monotherapy, there is no exhaustive list of all physicians who have prescribed or administered CPA monotherapy from which to draw a sample; hence, it is not possible to select a random sample of all physicians. Therefore, the study participants may not necessarily represent all physicians who have prescribed/administered CPA monotherapy. However, to the extent possible, information for respondents and nonrespondents will be evaluated to assess if there are any differences in available characteristics (e.g., geography, specialty, sex, years in practice).

In general, physician response rates for surveys have been somewhat low historically. In Germany, for post-authorisation safety studies, the German Medicinal Products Act (§ 67 Abs. 6 AMG, § 63f AMG) requires that physician participation in the study, as well as any associated compensation, be reported to the Federal Association of Panel Doctors, the Central Federal Association of the Health Insurance Funds, and the German Association of Private Health Insurance Funds. To meet this reporting requirement, physicians must provide their name and lifelong physician identification number as part of the survey. As a result, it is anticipated that the physician response to the survey may be particularly low in Germany.

Low response rates may result in a higher likelihood that participating physicians are not representative of all prescribing physicians. Thus, the resulting estimates of physician understanding about CPA monotherapy may be biased. If participants discontinue the survey because they do not know how to answer the knowledge questions, the frequency of substantial physician knowledge will be overestimated. Data will be collected to assess the number of physicians who begin but do not complete the questionnaire. This information can be used to help assess this potential bias. However, in our experience, almost all participants complete all items of the questionnaire.

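### Each knowledge percentage counts only physicians who answered that item; the protocol says this overstates knowledge if physicians quit because they do not know, yet it plans no bound on the effect

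*Protocol*

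**What the plan says.** Section 9.1.1 makes the percentage answering each knowledge question correctly the primary endpoint. Section 9.7 then fixes three rules for that percentage:

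- Denominator: "each question will be analysed individually among those participants who respond".
- Analysis population: eligible, consenting respondents who "completed at least one of the knowledge questions".
- Missing answers: "No imputation of missing data will be performed".

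Section 9.2.2 lets physicians stop at any time without a reason. On the consequence, Section 9.9 says: "If participants discontinue the survey because they do not know how to answer the knowledge questions, the frequency of substantial physician knowledge will be overestimated". The planned response is "Data will be collected to assess the number of physicians who begin but do not complete the questionnaire", followed by "This information can be used to help assess this potential bias". Section 9.9 adds that, in the study team's experience, nearly all participants finish; Section 9.7 likewise expects mostly complete data. Neither section gives a rate.

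Section 9.7.1 sets no formal target but calls 60% of respondents correct on each question reassuring.

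**The concern.** Under these rules, an eligible, consenting physician who stops before completing any knowledge item leaves the analysis altogether. One who stops later leaves the denominator of every item after that point. If lack of knowledge is what makes physicians stop, those removed are the ones who would have answered wrongly, and the percentage that remains is too high. The error would run towards reassurance about a serious risk, on the primary endpoint.

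Section 9.9 recognises this mechanism, but nothing in the protocol carries it into the results. A total count of non-completers does not show which items are affected or by how much. The stratified checks in Section 9.7 (age, gender, practice setting, type of physician) address imbalance in characteristics. They cannot detect physicians who stop for lack of knowledge within the same stratum.

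**Working it through.** **The plan's own figure.** Table 2 in Section 9.5 gives exact 95% limits of 81.9% to 87.8% for 85% correct among 600 physicians. Clopper-Pearson limits for 510 of 600 give the same values, and all 14 rows of the table reproduce to one decimal. The precision figures are correct. They describe sampling error only and make no allowance for unanswered items.

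**Inputs.**
- p: percentage correct among those who answered the item (Section 9.7 rule).
- d: share of the wider denominator that left the item unanswered. The protocol gives no figure, so 1% to 20% is an assumed range.
- q: percentage of non-answerers who would have been correct. This is unknown.
- 60%: the level called reassuring in Section 9.7.1.

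**Formula.** Percentage correct over everyone = p × (1 − d) + q × d. The overstatement is p minus this, which is d × (p − q). It is zero if non-answerers know as much as answerers (q = p). It is largest, at d × p, if none of them knows the answer (q = 0). The worst case is therefore p × (1 − d).

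**Worst case (q = 0), in per cent:**

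| d | p = 62 | p = 65 | p = 85 | p needed for 60% of everyone, 60/(1 − d) |
|---|---|---|---|---|
| 1% | 61.38 | 64.35 | 84.15 | 60.6 |
| 2% | 60.76 | 63.70 | 83.30 | 61.2 |
| 5% | 58.90 | 61.75 | 80.75 | 63.2 |
| 10% | 55.80 | 58.50 | 76.50 | 66.7 |
| 20% | 49.60 | 52.00 | 68.00 | 75.0 |

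**Break-off at which an item falls to 60% in the worst case, d = 1 − 60/p:**
- p = 62: 1 − 60/62 = 3.2%
- p = 65: 1 − 60/65 = 7.7%
- p = 85: 1 − 60/85 = 29.4%

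**Comparison with the reported interval.** Take 600 physicians in the denominator, d = 5% (570 answer) and 484 correct:
- Among those who answered: 484/570 = 84.9%, exact limits 81.7% to 87.8%, half-width about 3 points.
- Over all 600: 484/600 = 80.7%, exact limits 77.3% to 83.8%.

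The shift of 4.2 points exceeds the half-width, so the planned interval would not convey this uncertainty. At d = 1% to 2% the shift at p = 85 is 85 × 0.01 to 85 × 0.02, or about 0.9 to 1.7 points, which lies inside it.

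**The case against.** Several counter-arguments have force.

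- **The bias is disclosed and the data to examine it will be collected.** This stands. What is missing is a stated use of the count in the results.
- **Break-off is expected to be rare.** This is the only evidence on size in the document. If it means 1% to 2%, an observed 62% stays above 60% even in the worst case. The expectation carries no figure, however, so it limits the likely size without settling it.
- **Details and tables belong to the SAP.** Section 9.7 does defer them, and the SAP, which is not at hand, may add such an analysis. But the denominator, the population and the no-imputation rule are set in the protocol itself, and the point concerns those rules.
- **The 60% level is not a threshold.** Correct: Section 9.7.1 disclaims formal targets, Section 9.7 reads results qualitatively, and the 60% is expressed per respondent. No stated decision turns on one item moving from 62% to 59%.
- **Counting missing as wrong can be unfair.** Section 9.9 says German physicians must give their name and lifelong identification number, and some may leave over that. Branching (Section 9.1) and country adaptations (Section 9.3) mean some items may never be shown. A denominator of everyone who opened the questionnaire would score these cases as lack of knowledge, so it is too wide.

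A reader might also infer that the bias is certain, has a known direction and grows for later items. The documents do not support that. The statement in Section 9.9 is conditional, reasons for stopping are not recorded, and the questionnaire, with its item order and any don't-know option, is a separate document not shown. The statement in Section 9.3 that "respondents will not be able to move backward in the survey" concerns changing answers, not break-off.

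**Conclusion.** The concern holds in conditional form. The protocol fixes a respondents-only denominator for its primary endpoints, names a mechanism by which this would overstate knowledge, and provides no bound. The worst-case overstatement is d × p. For an observed 62% it is 0.6 points at 1% unanswered, 1.2 at 2%, 3.1 at 5% and 6.2 at 10%. It is minor if completion is as high as expected. It becomes material from about 5%, or sooner for items just above 60%.

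These figures rest on an assumed break-off rate and on every missing answer being not correct, so they are upper limits on the overstatement, not estimates of it. They do not show that the planned percentages will be wrong, and they do not justify replacing them as the main result.

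**What to change.** In Section 9.7:

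1. Keep the planned percentage among those who answered as the main result.
2. Add, for each knowledge item, a sensitivity analysis labelled as worst case. The denominator is all eligible, consented physicians who reached the knowledge section and to whom the item applied, leaving out items not shown because of branching or country adaptation. Unanswered items count as not correct.
3. Report the number reaching and the number answering each item.
4. Report separately the physicians who left before the first knowledge item, without scoring them.
5. Where an item reaches 60% only among those who answered, say so when describing it as reassuring. The bound informs that wording and is not a pass/fail rule.

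The cost is one more column in the knowledge tables and slightly less favourable figures beside the main ones. Section 9.9 already plans to collect the number who begin but do not complete. The web system would also need to record the item at which each physician stopped, which should be confirmed before data collection starts.

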9.7.1 Statistical considerations

No *a priori* thresholds of correct responses to the questions are established as targets for this study given the variability in prescriber specialty and indication. However, having a minimum of 60% of respondents selecting the correct response for each question would be considered reassuring regarding physician awareness and knowledge of the product's safety information. In a review of survey-based studies evaluating the effectiveness of risk minimisation measures in Europe, most participants responding correctly was considered a successful result in 9 of 11 surveys registered in the EU PAS Register (6).

9.8 Quality control

9.8.1 Data quality

will be responsible for EDC system development, quality control, and verification of the data collection. PPD will be responsible for data analysis and data transfer to Bayer.

Detailed information on checks for completeness, accuracy, plausibility, and validity will be given in the DMP, which will be available upon request.

National and international data protection laws as well as regulations on observational studies will be followed.

9.8.2 Quality review

This project will be conducted in accordance with the guidance described in Section 10.2 (regulatory authority approvals/authorisations) and the internal standard operating procedures of participating institutions. The PPD Office of Quality Assurance (OQA), an independent unit that reports to the vice president of PPD , will oversee quality assurance for this study.

Standard operating procedures will be used to guide conduct of the study. These procedures include internal quality audits, rules for secure and confidential data storage, methods to maintain and archive project documents, quality-control procedures for programming, standards for writing analysis plans, and requirements for senior scientific review.

All programming written by one study analyst will be independently reviewed by a different analyst, with oversight by a senior statistician. All key study documents, such as the analysis plan, questionnaire, and study report, will undergo quality-control review, senior scientific review, and editorial review.

For PPD , the OQA will perform audits and assessments that involve various aspects of the project, including but not limited to education and training documentation, data entry, data transfer procedures and documentation, and institutional review board (IRB) documentation. Such audits will be conducted by the OQA, according to established criteria in standard operating procedures and other applicable procedures.

A communication plan will be prepared to identify communication roles and responsibilities of key stakeholders and to describe the procedures for communicating the intent and conduct of the study.

9.8.3 Storage of records and archiving

All data for the physician survey will be electronic. Bayer will ensure that all relevant documents of this study will be stored after the end or discontinuation of the study for at least 15 years. Any data as well as programmes from statistical programming performed to generate results will be stored within the programming system for at least 15 years.

9.9 Limitations of the research methods

As with all cross-sectional surveys that depend on health care professionals agreeing to participate, some limitations are inherent. Many methodologic and operational challenges are well recognised (7). Although the study is designed to select a diverse and generally representative sample of physicians who have recent experience with CPA monotherapy, there is no exhaustive list of all physicians who have prescribed or administered CPA monotherapy from which to draw a sample; hence, it is not possible to select a random sample of all physicians. Therefore, the study participants may not necessarily represent all physicians who have prescribed/administered CPA monotherapy. However, to the extent possible, information for respondents and nonrespondents will be evaluated to assess if there are any differences in available characteristics (e.g., geography, specialty, sex, years in practice).

In general, physician response rates for surveys have been somewhat low historically. In Germany, for post-authorisation safety studies, the German Medicinal Products Act (§ 67 Abs. 6 AMG, § 63f AMG) requires that physician participation in the study, as well as any associated compensation, be reported to the Federal Association of Panel Doctors, the Central Federal Association of the Health Insurance Funds, and the German Association of Private Health Insurance Funds. To meet this reporting requirement, physicians must provide their name and lifelong physician identification number as part of the survey. As a result, it is anticipated that the physician response to the survey may be particularly low in Germany.

Low response rates may result in a higher likelihood that participating physicians are not representative of all prescribing physicians. Thus, the resulting estimates of physician understanding about CPA monotherapy may be biased. If participants discontinue the survey because they do not know how to answer the knowledge questions, the frequency of substantial physician knowledge will be overestimated. Data will be collected to assess the number of physicians who begin but do not complete the questionnaire. This information can be used to help assess this potential bias. However, in our experience, almost all participants complete all items of the questionnaire.

As is true with most surveys, it is possible that participants who complete the questionnaire will differ from non-participants in characteristics measured in the questionnaire (e.g., knowledge of or reading the SmPC and DHPC). The direction and magnitude of such potential participant bias is not known.

In addition, the sample does not account for individuals who could not participate because of the mode of data collection (i.e., Internet access). However, it is anticipated that the vast majority of physicians will have Internet access.

The study will target 600 physicians. The majority of the analysis will focus on aggregated data across all countries. Although the report will display country-specific findings, there may be limitations with drawing country-specific conclusions.

Bayer anticipates initial distribution of the SmPC and DHPC through May 2020. The survey will be conducted after physicians have received the CPA monotherapy educational material and have had a chance to use the information in their practice, which allows for evaluation of how well they understand the safety information provided in the SmPC and DHPC and apply it to their practices.

9.10 Other aspects

Not applicable.

10. Protection of human subjects

10.1 Ethical conduct of the study

This study is an observational study to evaluate physicians' knowledge and understanding of key safety information, as well as their receipt and use of the SmPC and DHPC for CPA monotherapy. There is no patient involvement in the study. Epidemiological methods will be used for the analysis of the collected data.

10.2 Regulatory authority approvals/authorisations

The study will be carried out within an approved indication in accordance with guidelines and regulations of the European Medicines Agency (EMA), FDA and applicable local law(s) and regulation(s) (e.g., Regulation (EU) No 520/2012 (8)). Recommendations given by other organisations will be followed as well (e.g., EFPIA (9), European Network of Centres for Pharmacoepidemiology and Pharmacovigilance [ENCePP] (10)). International Council for Harmonisation—Good Clinical Practice (ICH-GCP) guidelines will be followed whenever possible.

In addition, the guidelines on good pharmacovigilance practices (Good Pharmacovigilance Practice [GVP] module VI (11) and since the study qualifies as a PASS, GVP module VIII (12, 13)) will be followed.

10.3 Independent ethics committee (IEC) or institutional review board (IRB)

In all countries where reference to an independent ethics committee (IEC)/IRB is required, documented approval and/or notification from appropriate IECs/IRBs will be obtained prior to study start. When necessary, an extension, amendment, or renewal of the IEC/IRB approval must be obtained and also forwarded to the study initiator and funder. The IEC/IRB must supply to the study initiator and funder, upon request, a list of the IEC/IRB members involved in the vote and a statement to confirm that the IEC/IRB is organised and operates according to applicable laws and regulations.

10.4 Physician formation and consent

Physicians who are interested in participating in the study will be required to provide electronic acknowledgement of informed consent before completing the web-based questionnaire.

10.5 Patient insurance

Not applicable.

10.6 Confidentiality

Bayer as well as all investigators ensure adherence to applicable data privacy protection regulation. Data are transferred in encoded form only. The entire documentation made available to Bayer does not contain any data which, on its own account or in conjunction with other freely available data, can be used to reidentify natural persons. The investigators are obligated to ensure that no documents contain such data.

Physicians will be given unique login information to complete the survey. The personal identifying information collected from physicians will be limited to that which is necessary for compensation purposes and to meet regulatory requirements for reporting payments made to physicians in each country, as applicable. Only deidentified data will be made available to Bayer. Thus, any reports generated will not contain any participant identifiers. Data will be provided to Bayer in aggregate only and will not be linked to individual physicians.

Study findings stored on a computer will be stored in accordance with local data protection laws.

11. Management and reporting of adverse events/adverse reactions

This study is not designed to collect information on individual adverse events (AEs) or adverse drug reactions, which are better collected using other study designs. Adverse events are not anticipated to be part of the web-based physician survey because there will be no open-ended questions, and survey questions do not identify experience with an individual patient. However, an AE could be reported to the interviewers during the cognitive pretesting interviews. The interviewers will undergo safety training prior to conducting the pretesting interviews.

Any unsolicited AE information received will be handled following the Guideline on Good Pharmacovigilance Practices (GVP) Module VI—Management and Reporting of Adverse Reactions to Medicinal Products (14) and in accordance with Directive 2001/83/EC, Regulation (EC) No. 726/2004 and Commission Implementing Regulation (EU) 520/2012. The process for safety reporting will be conducted according to the pharmacovigilance agreement between Bayer AG and PPD transposing the collaboration agreement between Bayer AG and the MAHs participating in the consortium.

12. Plans for disseminating and communicating study results

